fMRI is the most widely used of the minimally/non-invasive techniques for presurgical language mapping in children [11]. However, MEG is gaining increasing acceptance as a non-invasive method as an adjunctive part of the pre-surgical functional mapping procedure [12]. Especially for language identification in pediatric cases, the quiet environment of the MEG room and the head-motion-tracking methods available in recent MEG systems, increase the likelihood of success with language lateralization in young populations. Further, MEG allows examining both hemispheres simultaneously, which is especially useful in epileptic populations, in which language lateralization is more variable. MEG language localization studies have shown encouraging results with a wide variety of paradigms, especially in localization of receptive language areas that are well documented [13, 14] and validated [15, 16]. The suitability of MEG language lateralization protocols in adults as an alternative to the Wada procedure have been addressed with validation studies conducted using various methodologies and exhibit overall high concordance rates (about 86-92%) [17-20]. Language lateralization is calculated in both hemispheres by localizing dipole sources (equivalent current dipole, ECD model) accounting for late auditory evoked field (AEF) components (150-700 ms after stimulus onset). These late components localize to language-related areas (mainly within posterior temporal areas) of the brain regardless of the modality of stimulus presentation [21]. Depending on the activation task, the dipole sources can be used to identify the location of receptive (Wernicke's area) or expressive language-specific (Broca's area) cortex. The degree of hemispheric asymmetry in the duration or strength of activation can also be calculated as an index of hemispheric dominance for language functions. Estimations of language lateralization with MEG [22] have mainly been based on recognition memory tasks for spoken words [23] or by listening to synthesized vowel sounds [24]. Thus, most of the MEG language studies have focused on receptive language areas. However, other reports exist on frontal circuits in expressive language [25-27] and basal temporal areas during semantic language tasks (verb generation) [28, 29]. Recent MEG language studies have reported the feasibility of passive paradigms in children and adolescents under sedation [30] and during sleep [31]. A recent MEG study [32] uses a verbal memory and verbal fluency tasks showing activation of the left hippocampus and in Wernicke's area in favor of the left hemisphere. Authors found higher concordance rates between a verbal memory paradigm and language dominance in controls (using handedness as criterion) and in subjects with epilepsy (using fMRI or Wada as criterion), compared with a verbal fluency task. Only the concordance for verbal memory reached statistical significance, with 93% agreement. Previous studies in pediatric epilepsy have shown atypical language lateralization [33] and that the word recognition task is the only language comprehension task used in both children and adults that yields high concordance between MEG and the Wada test for language lateralization [22]. Despite all contributions of MEG in the assessment of language localization in typically developing individuals, studies in pediatric populations with epilepsy is still relatively small especially in single subjects, which is necessary for clinical utility.

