Working memory (WM) and executive functions are skills developed to deal with complexities in life and are necessary for effective and adaptive behaviors. WM is the cognitive system that entails maintaining information in mind over a short time to complete an activity. WM is one of the most important components of information processing. A dysfunction of the WM system may lead to problems in developing cognitive functions, including mental arithmetic, reading, decision making and reasoning. WM is constituted by three main components: the central executive, the phonological loop, and the visuospatial sketch pad. Each component works to store and manipulate information in a temporary short-term memory system that is essential to human memory [42]. Executive functions include the control and organization of complex cognitive operations that allow a person to plan strategies, solve problems, and modify behaviors as a result of new information. The frontal lobes play a crucial role in WM and epilepsy has an impact on working memory functioning [43]. Visuospatial working memory (VSWM) involves encoding, maintenance, and retrieval of object identity, particularly spatial position [44-47]. VSWM is especially important in children during letter/number recognition, reading, writing, and math by facilitating recall of shapes and colors as well as their positions and movements. Determination of hemispheric memory lateralization plays an important role in the presurgical epilepsy evaluation, and very few studies have been conducted in children. The comparisons between adults and children revealed a greater activation in large regions of the frontal, parietal and temporal lobes, basal ganglia, and cerebellum in adults, while children showed greater activity in several occipital regions [48]. In adults, verbal memory has been predominantly lateralized over the left temporal lobe and visual-spatial memory over the right hemisphere [49-51]. But in children with epilepsy, a clear pattern of hemispheric lateralization of visuospatial memory has not been thoroughly investigated and established, and more investigations are needed to further assess WM in epilepsy.

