### ***Statistical Analysis***

Overall: MEG and clinical parameters will be summarized as means, SD and ranges (for continuous and count data), as proportions (for binary and nominal data), or as proportions supplemented with mean scores (for Likert-scaled or other ordinal data). We will export the MEG

Title: Pediatric Language and Memory Mapping in Refractory Epilepsy using Magnetoencephalography

PI: [name]

Site: Arkansas Children's Hospital

source analysis parameters for further statistical analysis. This is a pilot study that will provide the preliminary sample size estimates to support future research.

**Hemispheric dominance:** Estimation of hemispheric dominance for language [69] and memory [68] will be calculated as the degree of activation of each hemisphere during performance of the task. We will derive an estimate of hemispheric dominance by calculating the difference in activation levels between the hemispheres.

**Group level:** For this pilot [research](#) study, we will perform a preliminary statistical analysis by comparing MEG source activations between hemispheres (left vs. right) with  $\alpha=0.05$  significance level using a research statistical software.

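### The only planned test pools left-right differences over children who may be lateralised in opposite directions, which dilutes the result and can give a misleading null

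*Combined protocol and SAP*

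**What the plan says.** Three parts of the Statistical Analysis section matter here.

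- The group-level paragraph states that "we will perform a preliminary statistical analysis by comparing MEG source activations between hemispheres (left vs. right"), at a 0.05 significance level. It names no test statistic, sidedness, index or stratification. No other inferential analysis is described.
- The paragraph on hemispheric dominance states: "We will derive an estimate of hemispheric dominance by calculating the difference in activation levels between the hemispheres". It gives no normalisation and no rule for classing a child as left, right or bilateral.
- The general paragraph states that "MEG and clinical parameters will be summarized as means, SD and ranges", and that the pilot is to supply sample-size estimates for later research.

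The Background and Rationale describes lateralisation in the target population. It says MEG examines both hemispheres at once, "which is especially useful in epileptic populations, in which language lateralization is more variable". It adds: "Previous studies in pediatric epilepsy have shown atypical language lateralization". On memory it says that "in children with epilepsy, a clear pattern of hemispheric lateralization of visuospatial memory has not been thoroughly investigated and established".

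Study Design and Procedures gives ten subjects and Study Population gives fifteen. The calculations below use both.

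**The concern.** A group comparison of left with right activation asks whether the average child is more active on one side. It does not ask whether individual children are lateralised. If some children are left-dominant and others right-dominant, their differences offset each other in the mean and also inflate the between-child SD. The test statistic is hit twice.

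Two things are at stake. First, a non-significant pooled result could come from a cohort in which every child is clearly lateralised. Second, the pilot is meant to inform the size of later studies. A standardised effect taken from the pooled difference would mainly reflect the mix of directions in these 10 or 15 children, not how well MEG detects lateralisation in a child.

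**Working it through.** The documents state no power, effect size or SD, so there is no figure of the plan's own to reproduce. The check asks how a pooled test behaves when direction is mixed.

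**From the documents:** alpha 0.05; a left-versus-right group comparison; n = 10 or n = 15.

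**Assumed:** a two-sided paired t test on left-minus-right differences. Every child is truly lateralised with magnitude m, in units of the SD among children who share a direction. A share q is right-dominant, and each child's direction is drawn independently. The main case is m = 2, with m = 1 and m = 3 as a range.

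**Formulae.** Under this model:

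- mean signed difference = m(1 − 2q)
- SD of the signed difference = √(1 + 4m²q(1 − q))
- standardised effect d = m(1 − 2q) / √(1 + 4m²q(1 − q))

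For m = 2:

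- q = 0: d = 2.0/1 = 2.0
- q = 0.1: d = 1.6/√2.44 = 1.02
- q = 0.2: d = 1.2/√3.56 = 0.64
- q = 0.3: d = 0.8/√4.36 = 0.38
- q = 0.4: d = 0.4/√4.84 = 0.18
- q = 0.5: d = 0

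**Power by simulation** (400,000 simulated studies per cell):

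| Share right-dominant | 0% | 10% | 20% | 30% | 40% | 50% |
|---|---|---|---|---|---|---|
| n = 15, m = 2 | 100% | 90% | 61% | 30% | 11% | 5% |
| n = 10, m = 2 | 100% | 76% | 45% | 22% | 9% | 5% |
| n = 15, m = 1 | 95% | 69% | 40% | 20% | 9% | 5% |
| n = 10, m = 1 | 80% | 51% | 29% | 15% | 8% | 5% |

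Stronger lateralisation barely helps once directions are mixed. With m = 3 and 30% right-dominant, power is 33% at n = 15 and 24% at n = 10. A Wilcoxon signed-rank test does no better: about 20% at n = 10, m = 2, 30% right-dominant. Not naming the statistic therefore does not change the conclusion.

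**Strength against direction.** With m = 2 the mean absolute difference is about 2.0 at every split, while the mean signed difference runs from 2.0 to 0. The information is in the data, but the pooled signed comparison does not use it.

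**Effect on later planning.** By normal approximation, 80% power at two-sided 0.05 needs n = (1.960 + 0.842)²/d² = 7.85/d². Using unrounded d, this is 19.4 at 80:20, 53.5 at 70:30 and 237.4 at 60:40, or about 20, 54 and 238 children. Every child in the model is equally and strongly lateralised throughout. Only the mix of directions changes.

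**The case against.** Several stronger readings are tempting, and the documents do not support them.

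- **That opposite lateralisation averages to nothing.** This is true only near an even split. At 90:10 with 15 children, power under the main assumption is still 90%. Elsewhere the accurate word is dilution.
- **That the protocol expects frequent reversal.** It says more variable and atypical, with no rate. Atypical may mean weak or bilateral dominance as well as reversed. For visuospatial memory it says the pattern is not established, which is lack of knowledge and not a prediction of opposite directions.
- **That a null would be reported as MEG failing to lateralise.** No section says so. The test is called preliminary, Aim 1 is feasibility, and no decision is tied to the p-value.

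The plan also has a partial safeguard. It derives a between-hemisphere difference and summarises MEG parameters by SD and range. In a cohort this small, a range running from clearly negative to clearly positive would show opposite directions.

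These objections limit the claim but do not remove it. A range rests on two children and does not say how many lie on each side. The one planned test remains insensitive to lateralisation that differs in direction, and nothing in the plan warns against reading its null as absence of lateralisation.

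It would also be tempting to ask for a formal permutation test of lateralisation strength, or for a multiplicity adjustment across the two tasks. The documents do not make a case for either. Preprocessing averages epochs before source imaging, so swapping hemisphere labels epoch by epoch would need single-epoch source estimates that are not planned. Such a test would also count any non-functional asymmetry as lateralisation. If child-level asymmetry centred on zero is assumed, with SD equal to the noise SD, it rejects about 48% of the time with 10 children and 60% with 15. In a preliminary pilot, adjustment for two tasks is a matter of preference.

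**Conclusion.** The point holds as a problem of dilution. The single planned test measures whether children share a direction, in a population where the protocol itself gives reason to doubt that they do. If 20% to 30% of strongly lateralised children are right-dominant, power is about 61% to 30% with 15 children and 45% to 22% with 10. The standardised effect falls from 2.0 to between 0.64 and 0.38.

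These sizes rest on assumptions: equal lateralisation of 2 noise SDs in every child, no bilateral children, and a paired two-sided t test. The share of right-dominant children is unknown, so the result is a range and not a forecast for this cohort. The direction of the conclusion is the same for m = 1 to 3 and at either stated sample size.

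The change should be made before results are seen. The data would remain recoverable without it, so this is a weakness of analysis and reporting and not a flaw in the design.

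**What to change.** In the Statistical Analysis section:

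1. Name one between-hemisphere index per task (language, memory), including how it is normalised.
2. Show every child's signed index for each task, in a plot or listing.
3. Report the number lateralised each way with an exact 95% CI, and state in advance how a child is counted, including whether there is a bilateral category. For illustration, 12 of 15 in one direction gives 52% to 96%, and 8 of 10 gives 44% to 97%.
4. Report the mean absolute index as a descriptive measure of strength. It is not zero when there is no lateralisation: under pure normal noise its expectation is √(2/π) ≈ 0.80 noise SDs. It should not be presented as a test.
5. Report the pooled signed left-right difference as an estimate with a 95% CI, and state that a non-significant pooled result will not be read as absence of lateralisation.
6. Give the signed and absolute summaries side by side when passing estimates to future sample-size planning.

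The cost is SAP wording and a little more reporting. All quantities come from the between-hemisphere difference already planned, so no extra participants, visits or recordings are needed. The small downside is that the pooled p-value is no longer the headline result.

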How epilepsy affects working memory performance is unclear but evidence suggest disruptions in the WM network [52]. MEG studies to examine the hemispheric lateralization of visuospatial memory circuitry prior to epilepsy surgery are severely lacking especially in children [53]. Importantly, visuospatial memory reorganization with seizure foci from the left and right hemispheres has not been investigated in detail. Although a significant role for the mesial temporal structure is suspected in visual-spatial memory, technological advances in MEG sufficient to detect hippocampal dynamics has become possible only recently [41]. Importantly, cortical stimulation and the Wada procedure cannot identify memory-specific circuitry or language circuit interactions whose activity patterns are developing in a non-typical brain environment due to on-going epileptic activity. Moreover, both cortical stimulation and the Wada are intimately related to the narrow time window and not suitable for delineation of neural pathways during complex tasks, and the repetition of these procedures to detect reliability cannot be performed.

Title: Pediatric Language and Memory Mapping in Refractory Epilepsy using Magnetoencephalography

PI: [name]

Site: Arkansas Children's Hospital

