### **Aim 2**

Characterize language and memory circuitry in pediatric epilepsy subjects with seizure focus from the right or left hemispheres.

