## **Study Design and Procedures**

This is a pilot research study where we will design, develop and implement language and working memory tasks to study brain activities from children with epilepsy. Specifically For language assessment, a well known MEG language protocol will be used and novel signal processing techniques will be applied. We will use a design and implement a newwidely utilized paradigm to study memory function and adapt signal-processing techniques from previous literature for the processing and analysis of MEG signals collected during memory task. We will perform a MEG scan and collect data from ten pediatric subjects with drug-resistant focal epilepsy

Title: Pediatric Language and Memory Mapping in Refractory Epilepsy using Magnetoencephalography

PI: [name]

Site: Arkansas Children's Hospital

under evaluation for resective surgery. If a MRI scan is available from medical records and images have the appropriate characteristics for MEG (see more specifications at MRI section) analysis, we will use MRI for MEG source reconstruction. If MRI is not available, we will perform one scan. MRI is necessary to obtain brain anatomy for high quality MEG source reconstruction. Quantitative parameters will be extracted from MEG data for evaluating language and memory functions. This is a pilot [research](#) study where we will test the feasibility of the recording of both standard language and [experimental-well-known](#) memory task in patients with epilepsy. This research is important to investigate, by a non-invasive means, possible patterns of language and memory organization that may in future guide surgery and limit potential loss of these functions.

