## **Study Population**

A total of fifteen (15) pediatric patients with drug-resistant focal epilepsy under evaluation for resective surgery will be recruited from the comprehensive epilepsy program of the Arkansas Children's Neuroscience Center. If the patient is eligible, they will be informed about this study during their routine clinic visits by their clinician, and asked if they are interested in participating. Those who express an interest will be provided with the informed consent form (ICF) approved by the UAMS Institutional Review Board (IRB). If they agree to participate, they will be scheduled for the research visit. Subjects will be compensated with a gift card of \$40 which will be given to the parent or guardian (for subjects under 18) or to the subject (if over 18) after completion of study procedures.

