## **Data Analysis**

### ***Preprocessing***

MEG data will be exported for further analysis from the acquisition computer to the signal processing research software, Brainstorm [66] (<https://neuroimage.usc.edu/brainstorm/>), which is an open-source application dedicated to the analysis of brain recordings. Next, data will band-pass filtered between 0.5Hz to 100Hz and a notch filter will be applied for power-line noise removal (60Hz, 2nd order IIR notch filter with zero-phase lag). We will perform visual inspection to mark bad channels and segments. Data will be preprocessed for eye-blink and electrocardiogram reduction using a signal-space projection (SSP) technique [67]. The corresponding triggers recorded during acquisition will be used to import MEG epochs in the time window ranging from -200s to +800s with respect to the trigger [68, 69]. Baseline correction will be applied on the 200s before the trigger. Next, we will average across epochs to obtain an ERF waveform per subject for the language and memory tasks. Resting state data will use for baseline source imaging.

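### Aim 2 is about side of seizure focus, but no planned analysis relates the MEG measures to focus side

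*Combined protocol and SAP*

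**What the plan says.** Aim 2 reads: "Characterize language and memory circuitry in pediatric epilepsy subjects with seizure focus from the right or left hemispheres". The Background and Rationale explains the interest in side. It says that in children with epilepsy "a clear pattern of hemispheric lateralization of visuospatial memory has not been thoroughly investigated and established", and that "visuospatial memory reorganization with seizure foci from the left and right hemispheres has not been investigated in detail".

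The Statistical Analysis section then plans three things:

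- **Overall:** summaries of MEG and clinical parameters (means, SDs, ranges, proportions). It adds: "This is a pilot study that will provide the preliminary sample size estimates to support future research".
- **Hemispheric dominance:** the difference in activation between the two hemispheres, for language and for memory.
- **Group level:** a preliminary analysis "comparing MEG source activations between hemispheres (left vs. right"), at a significance level of 0.05.

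Preprocessing averages epochs to "obtain an ERF waveform per subject for the language and memory tasks", so subject-level values will exist. Preprocessing, Source Imaging and Statistical Analysis do not mention the seizure focus or its side. The Inclusion Criteria require focal epilepsy but set no side and no quota by side. Data Handling and Recordkeeping lists epilepsy history, EEG and imaging results among the items collected, but not an assigned side of focus.

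**The concern.** Left and right mean different things in the two places. In Aim 2 they are the side of the seizure focus, a characteristic of the subject. In the group-level analysis they are the two hemispheres of the same brain, a within-subject factor. A contrast between hemispheres across all subjects asks whether the sample as a whole favours one hemisphere. It does not ask whether lateralization differs by focus side, and it does not describe either focus group.

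Two things are at stake. The first is the answer to one of the study's two aims. The second is the pilot's stated purpose of informing later sample sizes: a future study by focus side needs the between-group difference and the within-group SD, and no planned output gives either.

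**Working it through.** The plan gives no effect size, SD, power or expected split by focus side, so it has no figure to reproduce. The sample size is ten in Study Design and Procedures and fifteen in Study Population; both are used below. Effects and splits are assumptions. Effects are in units of the within-group SD of D, with normal data, equal variances and two-sided tests at 0.05.

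**1. What each quantity estimates.** Let D be left minus right activation for a subject, with mean dL in the nL left-focus subjects and dR in the nR right-focus subjects.

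- All-subject contrast: (nL × dL + nR × dR) / (nL + nR)
- By-side difference: dL − dR

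The section does not say which subjects enter the contrast; all of them is the natural reading and is used here.

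**2. Same contrast, different truths (5 left, 5 right).** The all-subject column is a one-sample t test on D (simulation, 200,000 replicates). The by-side column is a two-sample t test (noncentral t).

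| dL / dR | Expected contrast | Groups apart | All-subject test rejects | By-side test rejects |
|---|---|---|---|---|
| 0.5 / 0.5 | 0.5 | 0 | 29% | 5% |
| 0 / 1 | 0.5 | 1 | 22% | 29% |
| −0.5 / 1.5 | 0.5 | 2 | 9% | 79% |

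For example, (5 × 0 + 5 × 1)/10 = 0.5. As the groups move apart, the planned test rejects less often, because the separation is counted as noise. With 7 against 8, the by-side test rejects 5%, 43% and 95%.

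**3. Opposite shifts.** With group means of opposite sign and equal size, groups 0.5, 1 and 2 SD apart give all-subject rejection of about 4%, 3% and 0.6 to 0.8% (5/5 and 7/8 splits). The documents do not establish that shifts are opposite; this shows only what the test would do if they were.

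**4. Dependence on the recruited mix.** Take dL = 0 and dR = 1.

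- 10 left, 5 right: (10 × 0 + 5 × 1)/15 = 0.33; rejection 17%.
- 5 left, 10 right: (5 × 0 + 10 × 1)/15 = 0.67; rejection 59%.

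The biology is the same in both rows. If instead dL = −0.5 and dR = 0.5, rejection is about 6% at either split, so the size of this effect depends on the common mean.

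**5. Variance for a later study.** The expected all-subject variance, relative to the within-group variance, is 1 + Δ² × nL × nR / (n(n − 1)), where Δ is the distance between groups.

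- Δ = 1: 1 + 25/90 = 1.28 (5/5); 1 + 56/210 = 1.27 (7/8).
- Δ = 2: 1 + 4 × 25/90 = 2.11 (5/5); 1 + 4 × 56/210 = 2.07 (7/8).

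A by-side sample size calculated from the all-subject variance is inflated by the same factor.

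**6. What a by-side estimate would deliver.** The 95% CI half-width is t(0.975, n − 2) × √(1/n1 + 1/n2).

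| Split | Half-width (SD) |
|---|---|
| 5 / 5 | 2.306 × 0.632 = 1.46 |
| 3 / 7 | 2.306 × 0.690 = 1.59 |
| 2 / 8 | 2.306 × 0.791 = 1.82 |
| 7 / 8 | 2.160 × 0.518 = 1.12 |
| 3 / 12 | 2.160 × 0.645 = 1.39 |

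Power reaches 80% only at a difference of about 2.02 SD (5/5) or 1.57 SD (7/8). At 0.5 SD it is 11% or 15%.

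**The case against.** The strongest reply is that Aim 2 says characterize, not compare. On that reading no between-group test is owed, and the subject-level dominance estimates already go some way. One could even take the mention of right or left focus as simply naming the population. It stands that a formal test is not required. But a description by side still needs results by side, and the Background singles out left and right foci as a knowledge gap, at least for visuospatial memory.

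Focus side might appear among the clinical parameters summarized as proportions. That is possible, though it is not named, and a count of left and right foci would not connect side to any MEG measure.

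The section does not exclude running the contrast within each focus group, in which case the cancellation and mix arguments would fall away. That is true, but nothing in the text says so.

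Every effect size above is assumed, and with 10 to 15 subjects the by-side estimates are wide. The variance inflation at 1 SD apart is also small beside sampling error: with 8 degrees of freedom (5/5), a 95% interval for a variance runs from about 0.46 to 3.67 times the estimate. These points limit how much weight the scenarios can bear. They do not touch the algebra in step 1, and low precision is a reason to report estimates with intervals rather than to omit the aim.

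**Conclusion.** The concern holds. No planned output relates the MEG measures to focus side, and the one group-level contrast estimates a different quantity from the one Aim 2 needs. That conclusion rests on the text and on the algebra, not on any assumed effect.

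The size of the consequence does rest on assumptions. If the contrast pools all subjects, an expected value of 0.5 SD at 5 against 5 is compatible with focus groups 0, 1 or 2 SD apart. Cancellation in particular depends on opposite shifts, which the documents do not establish.

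This should be fixed, in proportion to the study: a preliminary analysis in a pilot, with no confirmatory claim and no added risk to participants.

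**What to change.** Add to the Statistical Analysis section, in words such as these: *For each task, the hemispheric difference will be listed per subject and summarized (n, mean, SD) by side of seizure focus. The between-group difference (hemisphere by focus side) will be reported with its 95% confidence interval. This analysis is exploratory.*

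Also:

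- State that focus side is assigned from the presurgical EEG and imaging record before the research MEG source analysis. Say whether findings from the standard-of-care MEG may inform it.
- List bilateral or undetermined foci separately.
- Keep the all-subject hemisphere contrast as descriptive. Recoding hemispheres as ipsilateral or contralateral to the focus is optional.
- Reconcile the two sample sizes, since they set the precision: Study Design and Procedures says the study will "collect data from ten pediatric subjects with drug-resistant focal epilepsy", while Study Population gives "A total of fifteen (15) pediatric patients with drug-resistant focal epilepsy".

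The cost is a few lines of text, a rule for assigning side, and one new item on the data form; the EEG and imaging results are already to be collected. The drawback is imprecision, and one group may be very small. If each side is equally likely, the chance that one group has three or fewer subjects is 34% with 10 subjects and 3.5% with 15 (exact binomial). At a 70:30 mix it is 66% and 30%. The results should be read as estimates with intervals, not as tests.
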